Primary Analysis. The dependent variable is the proportion of order sessions that contain at least one order that was retracted and reordered (an RAR event). Inference about effectiveness of the intervention will be based on a Wald test of the coefficient of an interaction term between study-arm assignment and an indicator of pre- or post-intervention time period. The estimate of effectiveness will be the odds ratio (exponentiated coefficient) reported with its 95% confidence interval. With randomization at the clinician level, patient and order session level attributes may not be evenly distributed across groups. To reduce confounding bias, covariates at these levels that are both differentially distributed in the study groups and associated with the outcome will be included in this primary analysis. Clinician-level covariates will likely be balanced across study groups by randomization and will be included in this primary analysis only if descriptive statistics show otherwise.

Missing Data. Due to the automatic functioning of the EHR, we expect there will be no missing data concerning Retract-and-Reorder events, the mode of intervention group vs. control group, or the clinician-level covariates. There may be sporadic missing information regarding the patient-level covariates. In a prior RAR data set consisting of 11.6 million order sessions, there were no missing observations for patient age, sex, or race. An indicator for Hispanic ethnicity was missing in just 4 records. With similar levels of missing data, we believe that restricting regression models to only include cases with complete data will not introduce appreciable levels of bias. If we find that any variables are missing for more than 1 record per 1,000 (after backfilling based on other records involving the same patient), we will extend our analyses to address this. We will presume the data are missing at random and will apply multiple imputation with chained equations.

Methods for Aim 1 and 2: Photograph Study

2-Arm RCT: Statistical Power/Sample Size. The overall design is a randomized trial, with order-session observations nested within randomized clinicians. The number of clinicians is a fixed attribute of the study site and is not subject to investigator control. Based on preliminary data, we assume that we will obtain data on 12,000 clinicians, with half randomized to each study arm.

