Over 2.5 years of observation, we will accrue an average of 5,000 order sessions per clinician, with a coefficient of variation of 1.27. We anticipate that the intra-clinician correlation for the outcome will be about 0.001. The most recently available analyses from NYP suggest that the wrong-patient order session rate (a weighted average of inpatient and outpatient rates) is about 130 per 100,000 order

sessions. Using a two-tailed test at the 0.05 significance level, this will provide >90% power to detect a 25% reduction in the wrong-patient order-session rate in the intervention group in the primary analysis.

2x2 Factorial RCT: Statistical Power/Sample Size. For our 2x2 factorial study, we did a statistical power simulation. We assumed, based on prior information from our studies and information reported by our collaborators elsewhere that approximately 8,268 clinicians would be randomized in 1:1:1:1 ratio to the four study arms (no photo, photo in Storyboard only, alert with photo only, photo in both Storyboard and alert). We assumed that clinicians would generate an average of 74 order sessions per month, with a Poisson distribution, and that data collection would continue for 1 year. We assumed based on our previous studies that the variance component (in the log-odds metric) at the clinician level would be 1.9 (corresponding to an intra-clinician correlation of 0.52). We assumed that the base rate of RAR events is 9 per 10,000 order sessions. We ran 400 simulations of our study under these assumptions to determine that we would have 91% power (95% CI 88%-94%) to detect an odds ratio of 0.75 (i.e., 25% reduction in RAR events) for either photo intervention (in Storyboard or in alert) compared to no intervention. Our power to detect an additional 15% reduction by the combination of photo interventions (both in Storyboard and in alert) compared to either alone is 99.8% (95% CI 98.6%-99.9%).

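### Epic power section: a log-odds clinician variance of 1.9 corresponds to an intra-clinician correlation of 0.37, not the stated 0.52, and the documents do not show which figure is wrong

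*Combined protocol and SAP*

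**What the plan says.** The section on power for the 2x2 factorial trial (combined protocol and SAP) lists the inputs to a simulation. They are about 8,268 clinicians allocated equally to four arms, 74 order sessions per clinician per month (Poisson), and one year of data.

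- Clustering: the "variance component (in the log-odds metric) at the clinician level would be 1.9 (corresponding to an intra-clinician correlation of 0.52").
- Event rate: "We assumed that the base rate of RAR events is 9 per 10,000 order sessions".
- Result: "We ran 400 simulations of our study under these assumptions to determine that we would have 91% power (95% CI 88%-94"%) for an odds ratio of 0.75, "for either photo intervention (in Storyboard or in alert) compared to no intervention".
- A second result concerns "an additional 15% reduction by the combination of photo interventions (both in Storyboard and in alert) compared to either alone is 99.8"%.

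The section gives no conversion formula, no SD and no fitted model. It does not say whether the base rate is an average over clinicians or the rate of a typical clinician. No other section states a variance component. The 2-arm (Allscripts) section gives an intra-clinician correlation of about 0.001, with no scale named.

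**The concern.** The plan names the scale (log-odds) and says the two clustering figures correspond. They do not. The simulations are said to have been run under the listed assumptions, so the pair is a declared input to the only power justification for the Epic trial. A reader who rebuilds the simulation from 1.9 uses a different clinician spread from one who starts from 0.52, and may reach a different power. What is at stake is whether the 91% belongs to the clustering that the team meant to assume.

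**Working it through.** **1. The plan's own conversion.** For a random-intercept logistic model with clinician variance v, the log-odds-scale ICC is v/(v + π²/3), and π²/3 = 3.290.

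- Forward: 1.9/(1.9 + 3.290) = 0.366. The stated 0.52 is not reproduced.
- Backward: v = (0.52/0.48) × 3.290 = 3.56, SD 1.89.
- Rounding of the variance: 1.85 to 1.95 gives ICC 0.360 to 0.372.
- Rounding of the ICC: 0.515 to 0.525 needs v from 3.49 to 3.64.
- If 1.9 is an SD: v = 1.9² = 3.61, and 3.61/6.90 = 0.523.

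**2. Other conversions, taking 1.9 as a variance.** A probit residual of 1 gives 0.655. A residual of π²/6 gives 0.536. The probability-scale ICC is about 0.005 to 0.011. Dividing by the logistic SD, π/√3 = 1.814, in place of its variance gives 0.512, and 0.505 to 0.518 over the rounding range of 1.9. That last route is itself an error, but it comes close to 0.52.

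**3. The stated interval.** 91% of 400 is 364, and the exact 95% interval for 364/400 is 87.8% to 93.6%. This matches the printed 88%-94%, so the interval covers simulation error only and says nothing about the input.

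**4. How far the choice can move the power.** Inputs from the plan: 8,268/4 = 2,067 clinicians per cell, 74 × 12 = 888 sessions each, OR 0.75 (|log OR| = 0.2877). Assumptions: one photo cell against no photo, one year of post-intervention data only, and two-sided alpha 0.05 (stated for the 2-arm trial). Power = Φ(|log effect|/SE − 1.96).

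Random-intercept analysis, 9/10,000 as the average rate:

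| Variance | SE | Power by formula | Check simulation, 2,000 runs (95% CI) |
|---|---|---|---|
| 1.9 | 0.0669 | 99.0% | 99.1% (98.5%-99.4%) |
| 3.56 | 0.0909 | 88.6% | 89.3% (87.9%-90.6%) |
| 3.61 | 0.0916 | 88.1% | 87.9% (86.3%-89.3%) |

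For example, 0.2877/0.0669 − 1.96 = 2.34, and Φ(2.34) = 0.990.

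Population-averaged analysis with cluster-robust errors, same average rate (marginal rate ratio about 0.75):

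| Variance | SE | Power by formula | Check simulation, 4,000 runs |
|---|---|---|---|
| 1.9 | 0.0813 | 94.1% | 93.7% |
| 3.56 | 0.1519 | 46.0% | 54.5% |
| 3.61 | 0.1543 | 44.8% | 53.7% |

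Random-intercept analysis, 9/10,000 as the rate of the clinician whose random effect is zero (u = 0): SE 0.0562, 0.0710 and 0.0714 at variances 1.9, 3.56 and 3.61, giving power 99.9%, 98.2% and 98.1%.

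**5. The 99.8% figure.** Take it plainly as OR 0.85 for both photos against one (|log OR| = 0.1625), with random intercept and average rate. The SEs are 0.0703, 0.0947 and 0.0954 at the three variances, and the power is 64%, 40% and 40%. None is near 99.8%, so the figure must mean something else that the section does not spell out.

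**The case against.** The strongest reply is that the sentence already ranks its two numbers. The assumed quantity is the variance, the correlation is only a gloss on it, and no SD appears anywhere. On that reading the simulation used 1.9, the 91% stands, and only the parenthesis needs correcting. This is the natural reading of the text, and it may well be true. It cannot be confirmed from the documents.

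The opposite inference is also tempting. An SD of 1.9 reproduces 0.52 almost exactly. Under a random-intercept analysis at the average rate, variance 1.9 overshoots the stated 88%-94% while 3.56-3.61 falls at its lower edge. A reader might conclude that an SD was simulated. The documents do not support that. Under a population-averaged analysis it is variance 1.9 that comes close to the stated power, and using the logistic SD in the conversion also lands near 0.52 while leaving 1.9 a true variance.

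It is fair to add that the power grid rests on choices the section leaves open: the model, the contrast and the meaning of the base rate. It is also open whether the simulated test was the one in the Primary Analysis section, a "Wald test of the coefficient of an interaction term between study-arm assignment and an indicator of pre- or post-intervention time period". The 45%-54% figures need both the larger variance and a marginal analysis, and nothing in the section commits to that combination. Finally, the document is dated 10/01/2024 and reports clinician communications at two sites as already sent, so this is a correction to the record. That limits the weight of the point but does not remove the contradiction.

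**Conclusion.** The mismatch is certain on the scale the plan names: variance 1.9 gives ICC 0.37, and ICC 0.52 needs about 3.56. Which figure is wrong, and which was simulated, cannot be determined from the documents.

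The consequence is conditional. If 1.9 was simulated as a variance, the error is confined to the parenthesis. If a value near 3.6 was simulated, the printed variance is wrong and the 91% belongs to a different assumption from the one stated. Under the assumptions in the working, the choice is worth about 10 points of power with a random-intercept analysis at the average rate. It is worth about 40 to 50 points with a population-averaged analysis, and under 2 points if 9/10,000 is the rate at u = 0 with a random intercept.

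Three stronger readings should be resisted:

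- **The Epic trial is underpowered.** Several readings consistent with the text give 88% or more at either variance, so the mismatch does not show this.
- **The 91% or the 99.8% reveals the input.** The 91% fits different variances under different models, and the meaning of the 99.8% is too unclear for it to serve as a check.
- **The 0.001 in the 2-arm section contradicts 0.52.** It carries no scale, and a small probability-scale correlation can coexist with a large log-odds-scale one.

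This should be fixed, as a wrong stated power input; it is not a design flaw.

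**What to change.** Check the simulation code for the value passed as the clinician effect and whether it was used as a variance or an SD. Then correct the pair to one of two forms: variance 1.9 with ICC 0.37, or SD 1.9 (variance 3.6) with ICC 0.52. If the value simulated was not the one the team intended, rerun the simulation and restate the power; otherwise the 91% can stay.

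The cost is one corrected number and possibly a changed power figure. The size of any change depends on the analysis model and cannot be assumed to be small. Naming the fitted model, the contrast and the meaning of the base rate would let a reader verify the result, but that is added reporting detail, separate from this correction. Nothing in the design changes.

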Aims 1 and 2—The hypothesis of the study is that displaying patient photographs in an EHR at the time of placing electronic orders will significantly decrease the frequency of wrong-patient orders. We will test this hypothesis with a randomized controlled trial using a 2-arm design in Allscripts, and a randomized 2x2 factorial design in Epic to determine the optimal configuration of patient photographs (Figure 1). The design at the different sites is based on the functionality of the EHR systems. In Allscripts, clinicians randomized to the intervention arm will be shown a verification alert with a patient photograph at the time of placing orders; clinicians randomized to the control arm will be shown the alert with an avatar indicating the patient's sex (Figure 2). Epic has the functionality to display a patient photograph in the banner at the side of the screen (called Storyboard in Epic) and in a verification alert at the time of placing orders (Figure 3). Therefore, in Epic clinicians will be randomized to one of four conditions: 1) no photo; 2) photo displayed in Storyboard only; 3) photo displayed in the alert only; or 4) photo displayed in both Storyboard and in the alert.

2-Arm Randomized Trial in Allscripts	
Alert with No Photo	Alert with Photo
2X2 Factorial Randomized Trial in Epic	
No Photo in Storyboard/ No Alert	Photo in Storyboard/ No Alert
No Photo in Storyboard/ Alert with Photo	Photo in Storyboard + Alert with Photo

Figure 1. Photo Study Designs

[figure not shown]

Figure 2. Verification Alert With vs Without Patient Photo. (not an actual patient)

[figure not shown]

Figure 3. Patient Photo in Storyboard and Alert. (not an actual patient)

Patient Inclusion Criteria. In this study, we will include all patients for whom an electronic order is placed during the study period at the study sites. At all study sites, all patients aged 1 year and older will be included. Obtaining a photograph at registration is standard procedure at the participating study sites. Patients are not required to provide written or oral consent to have their photograph taken, as the photographs are used as part of routine care. However, patients or their legal guardians may refuse.

Clinician Inclusion Criteria. Any clinician who can place an electronic order can potentially place an order on the wrong patient. We will therefore include in the study all clinicians who place an electronic order at the study sites during the course of the study period.

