Interim Analysis. To safeguard against the possibility that our intervention actually worsens (increases) the rate of RAR events, and to prevent unnecessary continuation of a study that is already conclusive, a data safety monitoring committee will conduct one interim review of the data. At the midpoint of the study, we expect 50% of the data to have been accrued. Using the Lan-Demets alpha spending procedure with symmetric O'Brien-Fleming boundaries, the stopping rule at the interim review will be a z-statistic of magnitude 3.0318 or greater.²¹ The associated nominal *P* value is 0.0024. Combined with a final analysis using a critical z-value of 1.9669 (nominal *P* = 0.0492), we will have spent our overall alpha of 0.05 at the end of the study. The effects of this interim analysis procedure on nominal statistical power (see above) is negligible, less than 0.5 percentage points, so no adjustments to data collection are needed to account for this.

Methods for Aim 3

Observations/Surveys. We propose conducting an evaluation to assess barriers and facilitators that impact the implementation of patient photos in the EHR system. We will use anonymous surveys and observations; no individual identifiers will be collected. The purpose of this evaluation is to 1) elicit staff feedback about their experience during the photo implementation and registration process, 2) elicit patient feedback on their reasons for declining to be a part of the photo implementation process in the EHR, and 3) document observations of the photo implementation and registration process. Staff and patients will be assured that participating in the study is completely voluntary and will not affect staff's professional standing in any way or the standard quality of care the patient receives. All responses will be shared only with research personnel and will have no identifying information. The surveys and observation tool are attached in the Documents section.

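### The 99.8% power for both photos versus either alone cannot stand beside the plan's own 91% for a larger effect; at the precision behind that 91% it is about 46%

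*Combined protocol and SAP*

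**What the plan says.** The section on power for the 2x2 factorial trial assumes that "approximately 8,268 clinicians would be randomized in 1:1:1:1 ratio to the four study arms", with 74 order sessions per clinician per month for one year and a base rate of 9 retract-and-reorder events per 10,000 sessions. It assumes that the "variance component (in the log-odds metric) at the clinician level would be 1.9 (corresponding to an intra-clinician correlation of 0.52").

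From 400 simulated trials it reports two results:

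- "91% power (95% CI 88%-94%) to detect an odds ratio of 0.75" for either photo intervention against none.
- Power for an "additional 15% reduction by the combination of photo interventions (both in Storyboard and in alert) compared to either alone is 99.8" per cent, with 95% CI 98.6% to 99.9%.

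It gives no larger sample, longer follow-up or different test for the second result. The Research Design section describes the Epic part as "a randomized 2x2 factorial design in Epic to determine the optimal configuration of patient photographs".

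**The concern.** Both figures come from one set of inputs and equal arms, yet the smaller effect is given the higher power. A 15% reduction is harder to detect than a 25% reduction. The arms compared (both photos, one photo) also have fewer events than the arms in the first contrast (one photo, none). As worded, the two figures cannot both be right.

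Both versus either alone is the comparison that shows whether a second photo adds anything, which is central to choosing a configuration. A reader who trusts 99.8% would take a null result there as near-proof that no 15% gain exists, with a miss rate of 0.2%. At the precision the plan itself implies, such a gain would be missed about half the time.

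**Working it through.** **Inputs.** From the factorial power section: 8,268 clinicians, so 8,268/4 = 2,067 per arm; 74 x 12 = 888 sessions per clinician; base rate 9/10,000; clinician-level term 1.9; stated correlation 0.52. That section gives no significance level, so I take the one stated for the 2-arm trial ("Using a two-tailed test at the 0.05 significance level"). Using the Interim Analysis value instead ("Combined with a final analysis using a critical z-value of 1.9669") still gives 46% in step 3.

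**1. Events per arm.** 2,067 x 888 = 1.835 million sessions. Expected events are about 1,652 (no photo), 1,652 x 0.75 = 1,239 (one photo) and 1,239 x 0.85 = 1,053 (both).

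**2. Precision behind the 91%.** For a Wald test, power = Φ(|ln OR|/SE − 1.960). Power of 91% at OR 0.75 implies SE = 0.2877/(1.960 + 1.341) = 0.0872.

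**3. Power for OR 0.85 at that precision.**

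- Both versus one single-photo arm: 0.1625/0.0872 = 1.86; Φ(1.86 − 1.96) = 46%.
- At the ends of the stated interval (88% and 94%), SE is 0.0918 and 0.0819, giving 43% and 51%. The miss rate is therefore 49% to 57%.
- Both versus the two single-photo arms pooled: SE = 0.0872 x √0.75 = 0.0755, giving 58% (53% to 63%).

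**4. What 99.8% would need.** SE = 0.1625/(1.960 + 2.878) = 0.0336. The information ratio is (0.0872/0.0336)² = 6.7. At SE 0.0336, OR 0.75 would have essentially 100% power, not 91%.

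**5. Power from the inputs, without using the 91%.** Two inputs can be read in two ways. On the logistic scale, a variance of 1.9 gives a correlation of 1.9/(1.9 + 3.29) = 0.37; the stated 0.52 needs an SD of 1.9, since 3.61/(3.61 + 3.29) = 0.52. The 9 per 10,000 may be the overall rate or the rate of a typical clinician (random effect zero). Expected information from a random-intercept logistic model with four arms gives:

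| 1.9 read as | Base rate read as | OR 0.75 vs none | SE, both vs one | OR 0.85, both vs one | OR 0.85, both vs pooled singles |
|---|---|---|---|---|---|
| SD | overall | 88.2% | 0.0954 | 40% | 50% |
| variance | overall | 99.0% | 0.0703 | 64% | 76% |
| SD | typical | 98.1% | 0.0730 | 60% | 73% |
| variance | typical | 99.9% | 0.0582 | 80% | 89% |

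Direct simulation (300 trials, overall rate) agrees. With SD 1.9 it gives 89.0%, 42.3% and 50.3% for the three power columns; with variance 1.9 it gives 98.0%, 59.7% and 72.0%. The plan's 99.8% is not reproduced under any reading with OR 0.85.

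**6. No clustering at all.** Pairwise SE = √(1/1,239 + 1/1,053) = 0.0419, power 97.2%. Pooled SE = √(1/2,478 + 1/1,053) = 0.0368, power 99.3%. But OR 0.75 versus none would then have SE √(1/1,652 + 1/1,239) = 0.0376 and power above 99.99%, so the 91% would fail.

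**7. Where 99.8% could come from.** 399/400 = 99.75%, with exact 95% CI 98.6% to 99.99%, which matches the printed figure. Two contrasts produce power of that size:

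- Both photos versus **no** photo, OR 0.75 x 0.85 = 0.6375: 99.9% at SE 0.0872, and 99.8% in the first model of the table.
- A further factor of 0.85 on top of two multiplied 0.75 effects. Both versus one is then 0.75 x 0.85 = 0.6375, and the first model gives 99.5%.

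**8. Detectable effect.** With 80% power, the smallest detectable OR for both versus one is exp(−(1.960 + 0.842) x 0.0872) = 0.78. Across the four models it is 0.765 to 0.85.

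**The case against.** The strongest reply is that the sentence can be read so that nothing conflicts. In a factorial model, an additional 15% may mean an interaction factor of 0.85 over and above two multiplied main effects. Both versus either alone is then OR 0.6375, and the SD 1.9, overall-rate model gives 88.2% and 99.5%, each inside its stated interval. This is a real candidate for what was simulated. It does not rescue the text, because it makes the combination 36% better than a single photo, and the sentence tells the reader 15%. If instead the power quoted were for that interaction term itself, it would be only 23% to 51%.

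Reading 15% as percentage points (combined OR 0.60, so 0.80 versus single) gives 64% to 97% pairwise and 76% to 99.2% pooled. The 99.2% arises only in the model where the 91% would be 99.9%.

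Three limits do stand:

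- The 46% takes the 91% as correct and as a one-arm-versus-one-arm figure. If the 91% were a main effect over all four arms, the pairwise SE would be √2 larger and the power about 26%.
- With 1.9 read as a variance, as printed, the models give 99.0% to 99.9% where the plan has 91%, so that anchor is itself uncertain.
- The Primary Analysis section rests inference on a "Wald test of the coefficient of an interaction term between study-arm assignment and an indicator of pre- or post-intervention time period". The factorial power section describes no pre-period data, so these checks use a post-period contrast between arms.

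The mismatch between 1.9 and 0.52 is a separate slip. It matters here only because it moves the recalculated power. Finally, the plan already reports odds ratios with 95% confidence intervals, which limits the harm.

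**Conclusion.** The 99.8% is wrong as written. For a 15% reduction with both photos against either alone, power is about 46% at the precision implied by the plan's 91%. Across the four readings of the plan's inputs it is 40% to 80% pairwise and 50% to 89% pooled. None reaches the plan's own lower limit of 98.6%. That the second figure must be below the first needs no model, only equal arms, a smaller effect and fewer events. The percentages rest on a two-sided 0.05 test and a post-period comparison.

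A misdescribed contrast is the likely cause, but that is inference. Whatever the cause, the plan states no valid power for this comparison. The 91% for each photo against none, which serves the main hypothesis, is not shown to be wrong, although the inputs as printed do not reproduce it.

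**What to change.** 1. State the contrast, the comparator and the combined-arm odds ratio that produced 99.8%, and relabel the figure accordingly.
2. State whether 1.9 is a variance or a standard deviation, correct the correlation to match, and say whether 9 per 10,000 is the overall or the typical-clinician rate.
3. Re-run the existing simulation for both photos versus either alone at OR 0.85, saying whether the comparator is one arm or the two single-photo arms pooled, and replace the 99.8% with the result.
4. Give the smallest odds ratio for both versus either alone that is detectable with 80% power.
5. Add that a non-significant result for this comparison does not by itself exclude a 15% gain and is to be read from its 95% confidence interval.

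The cost is one simulation run and a few sentences, and probably a less favourable stated power. Enrolment and conduct are unaffected.

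### The printed interim and final critical values (3.0318, then 1.9669) belong to 48% information, not the stated 50%, which gives 2.963, then 1.969

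*Combined protocol and SAP*

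**What the plan says.** The Interim Analysis section states that "a data safety monitoring committee will conduct one interim review of the data". On timing it says "At the midpoint of the study, we expect 50% of the data to have been accrued". It names the Lan-DeMets alpha spending procedure with symmetric O'Brien-Fleming boundaries, and then fixes the numbers: "the stopping rule at the interim review will be a z-statistic of magnitude 3.0318 or greater", with nominal P 0.0024. The section continues "Combined with a final analysis using a critical z-value of 1.9669" (nominal P 0.0492) and concludes that "we will have spent our overall alpha of 0.05 at the end of the study". It puts the power cost of the look below 0.5 percentage points.

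Two other sections bear on this. The 2-arm sample size section specifies a two-tailed test at 0.05. The Primary Analysis section bases inference on a "Wald test of the coefficient of an interaction term between study-arm assignment and an indicator of pre- or post-intervention time period".

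No section gives an information fraction other than 50%, and no sentence says that the boundaries will be recomputed.

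**The concern.** Once the spending function, the sidedness, the overall alpha and the information fraction are given, both critical values follow by calculation. The printed values do not follow from the stated 50%. A reader who applies the named method gets a different interim threshold, and the document does not explain the difference.

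At stake is the committee's decision rule. An interim |z| between 2.963 and 3.0318 is a stop under the named method at 50% and a continue under the printed number. Because the boundary is symmetric, this applies equally to a signal that photographs increase wrong-patient orders, which is one of the plan's stated reasons for the review.

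A related gap is that the plan counts data, while a spending function runs on statistical information for the coefficient being tested. For an arm-by-period interaction the two shares need not agree. The plan gives no pre-period length and does not say whether pre-period data count toward the 50%.

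**Working it through.** **Inputs.** From Interim Analysis: one interim and one final analysis, fraction t = 0.50, Lan-DeMets O'Brien-Fleming-type spending, symmetric boundaries, overall alpha 0.05. From the 2-arm sample size section: two-tailed test.

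**Formulas.**
- Two-sided alpha spent at fraction t, with 0.025 per side: α(t) = 4[1 − Φ(2.2414/√t)], where 2.2414 = z(0.9875).
- Interim value: c1 = z(1 − α(t)/2).
- Final value: c2 solves P(|Z1| < c1, |Z2| < c2) = 0.95 with corr(Z1, Z2) = √t.

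**The plan's own conversions.** |z| = 3.0318 gives two-sided P 0.00243, and 1.9669 gives 0.04919. The printed z and P values agree with each other, so this is not a misprint of one figure.

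**Boundaries by fraction.**

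| t | α(t) | c1 | c2 |
|---|---|---|---|
| 0.48 | 0.00243 | 3.0318 | 1.9669 |
| 0.49 | 0.00273 | 2.9967 | 1.9677 |
| 0.50 | 0.00305 | 2.9626 | 1.9686 |

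At t = 0.50, for example, 2.2414/√0.50 = 3.1698, so α = 0.00305 and c1 = 2.9626. Solving for the fraction that gives c1 = 3.0318 returns t = 0.47999. The plan prints the 48% row.

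**Alternative methods at t = 0.50.**
- Classical O'Brien-Fleming, two equal looks: 2.797, then 1.977.
- The spending function applied once to two-sided 0.05: 2.772, then 1.979.
- Power family with ρ = 3: 2.734, then 1.983.
- Hwang-Shih-DeCani with γ = −4: 2.750, then 1.981; with γ = −5: 2.895, then 1.972.

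None gives the printed pair.

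**Overall alpha of the printed pair.** It is 0.05000 at t = 0.48 and 0.04994 at t = 0.50.

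**Interim crossing chance and overall power.** Assumption: the interim carries exactly 50% of the information, so the interim mean of z is d√0.5. Here d = 1.960 + z(power) is the drift of a fixed design. The 91% row takes its power from the factorial sample size section ("we would have 91% power (95% CI 88%-94%) to detect an odds ratio of 0.75"); the 90% row is a reference value.

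| Fixed-design power | d | Crossing at 3.0318 | Crossing at 2.963 | Overall power, printed pair | Overall power, 50% pair |
|---|---|---|---|---|---|
| 90% | 3.2415 | 23.0% | 25.1% | 0.8992 | 0.8990 |
| 91% | 3.3007 | 24.3% | 26.5% | 0.9092 | 0.9091 |

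The largest gap in crossing chance at any effect size is 2.8 points, at d = 4.24 (48.7% against 51.4%). The power lost to the look is about 0.1 point with either pair, so the plan's statement of less than 0.5 points is right.

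**2-arm trial at its planned effect.** Inputs from its sample size section: 6,000 clinicians per arm, 130 per 100,000 order sessions reduced by 25% (0.0013 against 0.000975), intra-clinician correlation 0.001, and "we will accrue an average of 5,000 order sessions per clinician, with a coefficient of variation of 1.27".
- Design effect = 1 + [(1 + 1.27²)m − 1] × 0.001, which is 14.06 at m = 5,000 and 7.53 at m = 2,500.
- For a simple arm comparison, expected |z| is 9.96 at the end and 9.62 at the interim.
- If the interaction doubles the variance (assumption), the interim value is 9.62/√2 = 6.80.
- Either boundary is then crossed with probability above 0.999.

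**Data share against information share.** In the same simple-comparison model, half the sessions carry (9.62/9.96)² ≈ 0.93 of the information, because the number of clinicians is fixed and only sessions per clinician grow. At t = 0.93 the spending function gives about 2.05, then 2.06. This figure does not carry over to the arm-by-period coefficient, where clinician effects may partly cancel. The documents do not allow that fraction to be derived.

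**The case against.** The strongest reply accepts the arithmetic and disputes its weight. Type I error is controlled at the stated fraction, power differs by about 0.02 points in favour of the printed pair, and the committee has an unambiguous prespecified number. This stands, and it keeps the point minor.

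A second reply is that 50% is only an expectation and that the Lan-DeMets method lets the boundary follow the observed fraction. The method does allow this, and the plan does not forbid it. But the plan prints fixed four-decimal values as the rule and does not say that they will be updated. Nor does this explain why the values printed next to 50% are those for 48%.

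A third reply has real force: the true fraction for the tested coefficient is unknown and could be far from either figure, as the 0.93 result for a simple comparison shows. Replacing a 48% number with a 50% number would then settle little by itself. That is a reason to treat the recomputation sentence as the more useful part of the fix, but it does not remove the mismatch. It also means that the crossing chances above hold only if the interim carries 50% of the information. The factorial power figure behind the 91% row compares each photo display with none and mentions no pre-period, so it may not describe the interaction test.

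**Conclusion.** The concern holds, as a minor error. The printed critical values contradict the stated 50% fraction under the plan's own named method. The interim threshold is 0.07 z-units stricter than that method gives (3.0318 against 2.9626) and the final one is 0.002 looser (1.9669 against 1.9686).

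At 50% information the net effect is slightly conservative. It lowers the chance of stopping at the interim by about 2 points for an effect with 90% or 91% power, and it makes no practical difference to the 2-arm trial at its planned 25% reduction.

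The boundary result rests only on inputs in the plan. The crossing and power figures assume 50% information, and the 2-arm figure for the interaction assumes a doubled variance.

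**What to change.** 1. In Interim Analysis, and in the committee's stopping rule, make the fraction and the boundaries agree. Either print 2.963, then 1.969 (nominal P 0.0031 and 0.0490) for 50%, or keep the present values and state 48% if that is the planned fraction.
2. Add one sentence: both critical values will be recomputed from the same spending function if the observed information fraction for the arm-by-period coefficient differs from the planned one.
3. State whether the 50% counts pre-period data.

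The cost is wording only. If the 50% pair is adopted, the higher final critical value costs about 0.02 percentage points of power at 50% information. Data collection does not change.
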